## 4 SAMPLE SIZE

The total sample size will be approximately 324 subjects (162 subjects per treatment arm). This is based on the following assumptions:

- A two group continuity corrected Chi square test with a 0.05 two-sided significance level will have 80% power to detect the difference between a placebo response rate of 20.0% and a voclosporin response rate of 34.4% (odds ratio=2.1) when the sample size in each group is 162 (total N=324).
- The effect of withdrawals will be investigated. Subjects withdrawing for any reason will be counted as non-responders in the primary analysis and therefore no adjustment of sample size for withdrawals is necessary.
- The impact of withdrawals on primary endpoint will be investigated in the tipping point analysis.

Table 4.1 shows the voclosporin response rates required to maintain a minimum 80% power at the planned sample size for given placebo response rates. These response rates all lead to odds ratios of around 2, which is a clinically relevant effect.

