## **5 RANDOMIZATION**

All subjects enrolled must be identifiable throughout the study. The Investigator will maintain a list of subject numbers and subject names to enable records to be found at a later date. Subjects will be allocated a subject number at the screening visit and registered with an interactive central randomization system. Subjects meeting the required eligibility criteria will be randomized to treatment at Visit 2 (baseline).

The randomization will be stratified by biopsy class (Class V only versus Others) and by prior MMF use at time of screening. The subjects will be randomized in a ratio of 1:1 to receive either voclosporin 23.7 mg BID or matching placebo. To help ensure balance, a centralized randomization will be utilized where region will be employed as a blocking factor. This will ensure balance between treatment groups within each of the 4 regions: North America, Latin America, Europe / South Africa and Asia Pacific.

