#### **6.13.1.1 Exposure-adjusted incidence rates**

Additional tables of exposure-adjusted incidence rates (EAIR) for certain groups of adverse events will be provided. The exposure for a given preferred term will be calculated for each treatment group as the total time at risk of an event. Each subject will have their exposure ( $t_i$ ) calculated with the exposures being summed to generate an overall exposure ( $T$ ) for the event in question for each treatment group. Exposures will be calculated differently depending on whether the subject did or did not experience the event in question.

For subjects experiencing the event in question exposure is calculated as the number of days from first dose of study drug to the time of the event.

For subjects not experiencing the event in question exposure is calculated as the number of days from first dose to the end of the study.

Incidence rates (IR) for each preferred term are calculated within treatment group as the number of subjects ( $n$ ) experiencing the event divided by the total time at risk for all subjects in the treatment group. Exposure-adjusted incidence rates will be displayed as the number of events / 100 years of exposure. The difference (voclosporin minus placebo) between the exposure adjusted incidence rates along with a 95% CI for the difference will be reported for each preferred term using the normal approximation [3].

$$EAIR = \frac{n}{T} = \frac{n}{\sum t_i}$$

The test statistic is given by (v=voclosporin, p=placebo):

$$E = \left( \frac{n_v}{T_v} - \frac{n_p}{T_p} \right) / \sqrt{\frac{n_v}{T_v^2} + \frac{n_p}{T_p^2}}$$

The 95% CI for the difference in EAIR will be calculated as follows:

$$\left( \frac{n_v}{T_v} - \frac{n_p}{T_p} \right) - Z_{\alpha/2} \sqrt{\frac{n_v}{T_v^2} + \frac{n_p}{T_p^2}} \quad , \quad \left( \frac{n_v}{T_v} - \frac{n_p}{T_p} \right) + Z_{\alpha/2} \sqrt{\frac{n_v}{T_v^2} + \frac{n_p}{T_p^2}}$$

Using exposure adjusted incidence rates, the following tables will be provided:

- Treatment-Emergent Adverse Events by System Organ Class and Preferred Term using Exposure-Adjusted Incidence Rate [subjects (n), exposure and treatment comparisons]
- Serious Treatment-Emergent Adverse Events by System Organ Class and Preferred Term using Exposure-Adjusted Incidence Rate [subjects (n), exposure and treatment comparisons]

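### The Wald interval for exposure-adjusted rate differences has no sparse-count rule, so with few events and a higher true rate on voclosporin its upper limit is too low

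*SAP*

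**What the plan says.** SAP 6.13.1.1 defines the rate as "calculated within treatment group as the number of subjects ( $n$ ) experiencing the event divided by the total time at risk". For a subject without the event, "exposure is calculated as the number of days from first dose to the end of the study". The voclosporin-minus-placebo difference is then given "along with a 95% CI for the difference will be reported for each preferred term using the normal approximation [3".

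The printed formula is the difference plus or minus Z times the square root of n_v/T_v² + n_p/T_p². It applies to two tables, one for all treatment-emergent events and one for serious treatment-emergent events, each by system organ class and preferred term. The section gives no minimum count for showing the interval, no rule for zero counts and no score or exact alternative.

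The role of the tables is limited: "Additional tables of exposure-adjusted incidence rates (EAIR) for certain groups of adverse events will be provided". They were added in SAP version 2.0 after regulatory agency feedback.

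**The concern.** The variance is estimated from the observed counts. An arm with no affected subjects contributes nothing, and at 1 v 0 the whole width of the interval rests on one event.

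Such rows are to be expected. The plan has 162 subjects per arm followed for about a year. Even broad Phase 2 safety contrasts had small counts: deaths were 10, 2 and 1 in the low-dose, high-dose and placebo arms (protocol 1.2.4.2), and discontinuations for decreased GFR were 1 on placebo, 6 on low dose and 5 on high dose (protocol 1.2.5). Individual serious preferred terms will often be rarer.

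The upper limit of the difference tells a reader how large an excess on voclosporin the data still allow. If it is too low for sparse serious terms, the table suggests that larger excesses have been excluded when they have not.

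**Working it through.** **Exposure.** The documents give no person-time per arm, so it has to come from the sample size: "The total sample size will be approximately 324 subjects (162 subjects per treatment arm". That figure reproduces. For 20.0% v 34.4%, the uncorrected requirement is 149 per arm. The continuity correction gives (149/4) × [1 + √(1 + 4/(149 × 0.144))]² = 37.25 × 4.365 = 162.6, or 163 against the stated 162. Power at 162 is 79.9%. At 52 weeks each, 162 subjects give about 162 person-years. I assume T = 150 per arm and vary it from 130 to 162.

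**Wald upper limits at T = 150, per 100 years.**
- 1 v 0: difference 0.667, standard error √1/150 = 0.667; 0.667 + 1.96 × 0.667 = 1.97.
- 2 v 0: difference 1.333, standard error √2/150 = 0.943; 1.333 + 1.96 × 0.943 = 3.18.
- 2 v 1: difference 0.667, standard error √3/150 = 1.155; 0.667 + 1.96 × 1.155 = 2.93.
- 0 v 0: both limits are 0, so the interval has zero width.

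**Score upper limits.** The variance is taken at the two rates estimated under the tested difference D. With no placebo events, the constrained placebo rate at the upper limit is 0. Writing x = D × T, the limit solves (x − n)² = 3.8415x.
- n = 1: x = 5.665, and 5.665/150 = 3.78 per 100 years.
- n = 2: x = 7.293, and 7.293/150 = 4.86.
- 2 v 1 needs a numerical solution: 4.26.

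| Observed | Wald upper | Score upper | Ratio |
|---|---|---|---|
| 1 v 0 | 1.97 | 3.78 | 0.52 |
| 2 v 0 | 3.18 | 4.86 | 0.65 |
| 2 v 1 | 2.93 | 4.26 | 0.69 |

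With equal T both limits scale as 1/T, so the ratios do not depend on the 150. At 1 v 0 the pair is 1.83 v 3.50 with T = 162, and 2.28 v 4.36 with T = 130 (2.96/130 and 5.665/130). The methods converge as counts grow: at 20 v 10 and T = 162 the limits are 12.80 v 13.54.

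**How often the true excess lies above the upper limit.** I summed independent Poisson probabilities over all pairs of counts, given at least one event in either arm. The documents give no event rates by term, so the expected counts (voclosporin, placebo) are assumptions.

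| Expected counts | Wald, above upper limit | Score, above upper limit | Wald two-sided coverage |
|---|---|---|---|
| (2, 1) | 9.1% | 1.2% | 90.2% |
| (4, 1) | 8.8% | 1.8% | 90.3% |
| (5, 1) | 6.1% | 1.5% | 93.3% |

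The nominal figure is 2.5%. At (2, 1) the true excess is 1 event. Observing 0 v 1 gives an upper limit of −1 + 1.96 = 0.96 events, which just misses it. That one outcome has conditional probability e⁻³/(1 − e⁻³) = 5.2%, more than half of the 9.1%. Such dips are therefore local: with T = 150 and 145 and the expected counts scaled to match, the 9.1% becomes 3.9%.

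Over 72 scenarios with a higher voclosporin rate and at most 5 expected events, the conditional upper-limit error had median 4.3% and maximum 15.7%. Conditional coverage had median 94.8% and minimum 83.9%, and 11% of scenarios fell below 90%.

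**Equal true rates.** Wald coverage is 99.8% at (0.5, 0.5), 98.6% at (1, 1), 95.9% at (2, 2), 95.3% at (3, 3) and 94.8% at (10, 10).

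**The case against.** A reader might infer that this interval has coverage far below 95% for rare events in general. Enumerating all samples seems to show it: 42% at expected counts (0.5, 0.05) and 69% at (1, 0.2). The documents do not support that reading.

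Nearly all of that shortfall comes from samples with no event in either arm, with probability e^(−0.55) = 57.7% and e^(−1.2) = 30.1%, where the interval collapses to zero width. Given at least one event, coverage in those two scenarios is 100% and 99%. A preferred term that nobody reported would ordinarily have no row, although the visible SAP text does not say so. With equal true rates there is no deficit beyond a fraction of a percentage point.

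The other strong objection is that little hangs on these intervals. The type 1 error strategy in SAP 6.11.5 covers efficacy endpoints only, and no alpha, stopping rule or claim attaches to these tables. They show the number of subjects and the exposure beside the comparison, so a 1 v 0 row is visibly 1 v 0. SAP 6.13.1 also plans top-line risk differences, serious-event tables by region and period, and full listings.

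Both objections stand and limit the importance. They do not remove the defect in rows that would be printed. The limits at 1 v 0, 2 v 0 and 2 v 1 need no assumption about true rates, and the top-line risk differences are not given by preferred term.

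**Conclusion.** The point holds in a limited form. SAP 6.13.1.1 uses a Wald interval for every preferred term with no sparse-count rule. At very low counts its upper limit is about half to two-thirds of the score limit. When the true rate is higher on voclosporin, the chance of missing the true excess is often above the nominal 2.5%: typically about 4% given at least one event, and about 9% at (2, 1) and (4, 1). A claim that coverage is generally far below 95% for rare events is not justified.

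The result rests on Poisson counts, roughly equal person-time of 130 to 162 years per arm, assumed expected counts, and 0 v 0 terms not being displayed. Importance is modest, because these are additional descriptive safety tables.

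**What to change.** In SAP 6.13.1.1, replace the Wald interval with a score interval (Miettinen-Nurminen type) or an exact-based interval for the difference of two Poisson rates, and use it for every row so that the method does not depend on the observed counts. The definitions of n and T stay as they are. State also whether terms with no event in either arm are shown.

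The cost is one formula, a short macro and wider intervals for rare terms. The score interval is not exactly nominal either: its coverage ran from 93.1% to 100% in the scenarios checked, against 96.4% to 100% for an interval built from exact Poisson limits. A minimum count for printing the interval would be a simpler alternative, but it would leave the rarest serious terms with no interval.

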### 6.13.2 Laboratory Data

Descriptive statistics of the observed values and change from baseline (continuous data) will be presented by treatment group and visit for each hematology, urinalysis and serum chemistry

continuous parameter. Each measurement will be classed as below, within, or above normal range, based on ranges supplied by the laboratory used. Shift tables in relation to the normal range from baseline to each follow-up visit will be presented.

Analysis of all samples for hematology, chemistry, hepatic function, lipid profiles, and urinalysis will be performed at a central laboratory using standard validated methods (see the laboratory manual). All study data analyses involving laboratory values will be based on results from the central laboratory.

The table below shows the tests, parameters, and time points that will be summarized by treatment arm. For the screening time points, only the last non-missing measurements will be included in the summary.

**Table 6.5 Laboratory Parameters**

Test Type	Test Parameters	Time Points
Hematology	Complete blood count (CBC)	All except Day 2
	Hematocrit	
	Hemoglobin	
	Mean corpuscular hemoglobin (MCH)	
	Mean corpuscular hemoglobin concentration (MCHC)	
	Mean corpuscular volume (MCV)	
	Platelet count	
	Red blood cells (RBC)	
	Red blood cell morphology	
	White blood cells (WBC)	
	Differential (absolute and %)	
	Bands	
	Basophils	
Eosinophils		
Lymphocytes		
Monocytes		
Neutrophils		
Erythrocyte sedimentation rate	Day 1, Week 24, and Week 52	
Coagulation	Coagulation	Screening
	Activated partial thromboplastin time (aPTT)	
	Prothrombin time (PT)	
	Partial thromboplastin time (PTT)	

### **6.13.3 Vital Signs**

Descriptive statistics for observed values and changes from baseline in the following vital signs will be presented by treatment group and visit:

- Systolic blood pressure (mmHg)
- Diastolic blood pressure (mmHg)
- Pulse rate (bpm)
- Body temperature (degrees Celsius)

Mean values for systolic and diastolic blood pressure will be used in the summary tables. Where the mean value is unavailable, an individual measure at the visit in question will be used. Listings of all vital sign measurements will be provided.

### **6.13.4 Electrocardiogram Data**

Descriptive statistics for observed values and changes from baseline in the following ECG variables at screening, Week 12, Week 24, and Week 52 will be tabulated at each follow-up:

- Heart rate (bpm)
- PR interval (ms)
- QRS complex (ms)
- QT interval (ms)
- QTc interval (ms)
- QTcF interval (ms)

Shift tables in relation to the overall interpretation (Normal, Abnormal NCS, and Abnormal CS) from baseline to each follow-up visit will be presented. Listings of all ECG measurements will be provided.

### **6.13.5 Physical Examination**

Physical examination will be summarized for the safety population at timepoints: screening, Day 1 (Baseline), Week 24, and Week 52. The following parameters will be summarized: Height (as part of demography at screening only) and Weight.

Physical examination results with clinically significant abnormalities (Yes/No) will be listed.

## **7 INTERIM ANALYSIS**

There are no planned interim analyses. The analysis of the primary endpoint (renal response at Week 52) will be conducted at the end of the study.

## **8 DATA AND SAFETY MONITORING BOARD ANALYSES**

Data and Safety Monitoring Board (DSMB) analyses are detailed in a separate DSMB charter and associated documents.

## 9 CHANGES TO PLANNED PROTOCOL ANALYSIS

In the randomization, regional differences were not expected and blocking by region was done more for drug distribution reasons. While the analysis specified in the protocol stipulated that the regional blocking factor was not to be used in the analysis models, following feedback from regulatory agencies, the models will include terms for each of the factors used in the randomization process:

- Biopsy Class (Class V versus Others)
- MMF use at screening (Yes versus No)
- Region (North America, Latin America, Europe+South Africa and Asia Pacific)

During the regulatory agency review and feedback process it was decided to remove the ‘Duration of UPCR  $\geq 0.5$ ’ endpoint from the list of key-secondary endpoints and place it within the list of ‘Other Secondary Endpoints’. The proportion of subjects experiencing a confirmed  $>30\%$  decrease from baseline in eGFR at each timepoint was also removed from the list of key secondary endpoints. To this end, neither endpoint will form part of the hierarchical testing procedure.

## 11 LIST OF TABLES, FIGURES AND LISTINGS
